15. Client Satisfaction Questionnaire (CSQ) (Attkisson et al. 1982) is an 8-item unidimensional measure of client satisfaction with services. Psychometric properties, operating characteristics, and coefficient alpha (.93) are very strong for this measure which we will collect from adolescents and parents.
16. Decision Making Involvement Scale (DMIS) (Miller et al., 2012): is a 30-item scale to measure adolescent involvement in a decision. The five subscales are: “Child Seek” (child asks for an opinion or information from parent), “Child Express” (child expresses an opinion or information to parent), “Parent Seek” (parent expresses advice or opinion to child), “Parent Express” (parent expresses advice or opinion to child), and “Joint/Options” (negotiation or brainstorming between parent and child). We will collect this measure from adolescents and parents.

DATA ANALYSIS

Hypothesis testing:

Each hypothesis examines part of the mechanism underpinning intervention impact on medication continuity.

Hypothesis #1: Adolescents will use greater than 80% of relevant intervention components. For each subject, we will calculate the proportion of **recommended** intervention components that were utilized by the subject during the study intervention period. The mean and 95% confidence interval (CI) will be computed to give a range estimate of the fidelity measure. To evaluate our hypothesis, we will utilize the computed CI to determine if 80% or greater is a plausible value, such that if the CI includes a value of 80% or greater we will reject the null hypothesis. We will also examine the temporal distribution of use for each of the recommended components.

Hypothesis #2: Use of the intervention components will be related to improvements in the targeted UTBC factors. Using a generalized linear model, we will test whether the intervention addressed the UTBC factors (i.e., pre-intention factor scales and ABMS/PBMS total and subscale scores). Model predictors will include a fixed effect indicator of time point (baseline or end of study). A significant effect of time point in the expected direction would indicate UTBC factor improvement.

Hypothesis #3: Medication continuity will be higher at the end of the study compared to the baseline period. We will compare the percentage of days covered with medicine using a paired t-test. In exploratory analyses, we will compare this cohort's percentage of days covered at end of study with the percentage of days covered in a control group that is accruing as part of another study (IRB# 2020-0236).

Hypothesis #4: Pre-post changes in UTBC factors will be related to increases in medication continuity. We will calculate the change score for each relevant UTBC factor (end of study minus baseline) and the change score for medication continuity (end of study minus baseline). We will model the association between change in UTBC factor scores (independent variable) with change in medication continuity (dependent variable) using generalized linear model. A significant effect of change in UTBC factor scores (beta coefficient) in the expected direction would indicate changes in UTBC factor scores were associated with medication continuity improvement.

Exploratory analyses:

We will conduct descriptive analyses to characterize rates of diversion at baseline and end of study using a McNemar's test to see if rates differ. We will summarize responses to the client satisfaction questionnaire descriptively as this may facilitate future dissemination.

Power and Sample Size:

We are adequately powered for our exploratory analysis of Hypothesis #3. The study would require a sample size of 18 for each group (i.e. a total sample size of 36), to achieve a power of 80% and a level of significance of .05 (two sided), to detect a difference in means between the intervention and the control groups of 15.7% (i.e. 66.2% vs. 50.5%) on the percentage of days covered with medicine assuming a pooled standard deviation of 16.5. Due to the low intra-class correlations observed in previous studies of ADHD medication continuity (ICC = 0; [name] et al. 2018), the analyses will not account for the nesting of patients within physicians. We will recruit 44 patients (22 in this cohort and 22 in control group from 2020-0236) to ensure that 36 are retained for this analysis. A retention rate of 80% (36/44) is conservative in light of the 12-month retention rate of 92% achieved by [name] in his current trial.

Scientific Rigor:

Our open label trial is an appropriate design to initially examine whether the intervention engages the mechanism underlying medication continuity and therefore warrants further testing in a future larger trial. Our preliminary data strongly supports the importance of the problem, intervention targets identified, and the feasibility of the approach in our hands.

FACILITIES

Cincinnati Children's Hospital is the performance site for this study.

POTENTIAL BENEFITS

Although we cannot guarantee a benefit to any individual participating pediatrician, adolescent, or parent, the intervention components we propose to integrate into the ADHD web portal are theory- and evidence-based strategies with significant support from the research and clinical literature. Thus, families have the potential to benefit from state-of-the-art treatment. Benefits of the study outweigh any potential risks because our interventions are likely to improve care and outcomes for children who receive them.

POTENTIAL RISKS, DISCOMFORTS, INCONVENIENCES, AND PRECAUTIONS

There is minimal risk to the participants in this study other than a potential for invasion of privacy. Because confidential information about study participants will be available to study staff, procedures to safeguard the confidentiality of this information are required. Given the sensitive nature of some of the teen-reported outcome measures (e.g. ADHD medication diversion), we will apply for a Certificate of Confidentiality that will allow collection of these measures but will protect this information from being divulged to other parties. Additionally, several safeguards will be put in place. All data collected on pediatricians, adolescents, and parents will be assigned a unique code that will be linked to identifying information. The master coding sheet that will link the information will be kept in the study coordinator's office under lock and key. In addition to assuring confidentiality of the research data, it is also critical that the confidentiality of the patient's clinical information is protected in mehealth for ADHD. The HIPAA regulations and their application to this product will be clearly defined to ensure compliance within their guidelines. Mehealth for ADHD was designed with a procedure for encrypting and storing the data in such a manner to only allow pediatricians to view identifiable data. This design employs a key-based encryption structure. This method does require extra security information to be maintained by the parties who are encrypting the data. For example, parties needing access to the data are assigned a "key" that is used to encrypt and decrypt the data in addition to a user ID. Such a key will be maintained by the PI and kept under lock and key. Implementation of additional methodologies to keep the confidential information off the server will be implemented including such methodology as ensuring the CCHMC server is secure (i.e., firewalled).

Data from this study may be submitted to the National Institute of Mental Health (NIMH) that allows researchers studying mental health and substance use to collect and share deidentified information with each other. If participants consent to have their information shared in the data repository, all personal information about research participants such as name, address, and phone number will be removed and replaced with a code number. Participants may decide at any point that they do not want to share their information to the NIMH data repository. If a family consents to have their data shared, the information required to create their deidentified code number will be collected during the phone screen by a member of the research team.

PROTECTION OF VULNERABLE POPULATION

Because children are being invited to participate in the study, the following procedures will be followed to avoid issues related to coercion or undue influence. First, study staff will review the consent form with participating children, in language appropriate for their intellectual functioning and developmental levels, and ask whether or not the child agrees to participate.

Similarly, they will be told that they can opt not to participate or answer any questions which they do not want to answer at any time. This will be re-iterated whenever necessary.

RISK/BENEFIT ANALYSIS

The risks to participants are minimal and unlikely, largely stemming from the possibility of loss of confidentiality. We have instituted provisions to minimize this risk and will assure participants of the voluntariness of their participation and their right to withdraw participation at any time. We will also take appropriate steps to safeguard confidentiality. We would suggest that this study falls under the "Minimal Risk" category.

ALTERNATIVES

Participation in the present study is completely voluntary. The alternative to participation in the study is to choose not to participate in the study.

DATA SAFETY & MONITORING

Intervention development will design and optimize the prototype intervention. Physicians, adolescents, and parents who agree to participate will receive access to mehealth for ADHD that has been enhanced with new intervention components. Given that the risks to participants are minimal, there does not appear to be the need for an external monitoring board. Rather, the Drs. [name] (PI) and [name] (co-I) will assume primary responsibility for the ongoing monitoring of the data and safety of the study, and will provide reports of this with annual renewal application to the IRB and annual progress report to the sponsor. Both are experts in ADHD management, ADHD research, and have experience conducting community-based research such as that proposed in this application. [name] has medical expertise related to pharmacotherapy of children with ADHD to address study-related medical issues. All research staff will complete education in the protection of human research subjects.

Drs. [name] and [name] will continuously evaluate the project's performance, safety, and need to stop. Performance will be monitored by examining subject recruitment, comparison with targeted recruitment retention, protocol adherence, and quality of data collection procedures. This will primarily be accomplished in weekly staff meetings attended by Drs. [name] and [name].

Drs. [name] and [name] will be available at all times to address any safety issues. Any serious adverse events will be determined by Drs. [name] and [name] and reported to the IRB within 24 hours, specifying the nature of the event and outcome, if related to the study and if anticipated or not. If a serious adverse event as a result of participation in the study occurs, recruitment will be immediately discontinued until the serious adverse event has been reported to the IRB and the IRB has deemed it appropriate for the study to continue.

COST OF PARTICIPATION

There will be no costs to the subject for participating in this study.

PAYMENT FOR PARTICIPATION

Each parent/adolescent dyad will be compensated \$50 for each survey completed during the trial for a total of \$100 throughout the intervention. We will pay \$250 per enrolled pediatrician at each practice to reimburse office staff members such as a nurse or office manager for identifying eligible subjects and obtaining their consent to be contacted by the

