Official Title of the study: **Web Based Tools to Improve Medication Continuity in Adolescents With ADHD**

NCT number: **NCT04173000**

Document name: **Statistical Analysis Plan**

Date of the document: **5/19/2022**

The results of the Web Based Tools study will be assessed as described in this document. This statistical analysis plan begins with an overview of the key components of the study, including its design, objectives, and outcomes measures. This is followed by a detailed description of the statistical analyses that will be utilized to address study hypotheses.

1. Overview of study: This study is a 4-month open label trial to test whether an intervention engages the mechanism underlying medication continuity and improves outcomes. Adolescents and their parents that agree to participate in the study will receive the intervention (MeHealth for ADHD software with medication continuity tools). We planned to enroll a total of 20 adolescents aged 11-15 with ADHD with poor medication continuity who receive care from one of the 24 pediatricians recruited from ~8 practices who currently use the MeHealth for ADHD portal.

1.1 Study Objective: Test a multi-component intervention that systematically identifies and targets aspects of the Unified Theory of Behavior Change (UTBC) model most relevant for each adolescent with poor ADHD medication continuity.

Working hypothesis 1: Medication continuity will be higher at the end of the study compared to the baseline period.

Working hypothesis 2: Use of the intervention components will be related to improved outcomes as measured by change in the Unified Theory of Behavior Change factors.

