1.3 Intervention Fidelity measures

- Fidelity to intended use of intervention components during the 4-month trial.
 - Proportion of intervention components completed relative to the components that were recommended by the portal based on adolescent/parent responses to the assessment battery.

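### The Hypothesis #1 rule accepts use above 80% whenever the upper 95% limit reaches 80%, and the later SAP drops both rule and interval without comment

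*Protocol*

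**What the plan says.** Under Hypothesis testing in the protocol's DATA ANALYSIS section, Hypothesis #1 reads "Adolescents will use greater than 80% of relevant intervention components". For each subject the plan takes the proportion of recommended components actually used, and then: "The mean and 95% confidence interval (CI) will be computed to give a range estimate of the fidelity measure". The interval is to be used to "determine if 80% or greater is a plausible value", and the sentence closes with the decision rule: "if the CI includes a value of 80% or greater we will reject the null hypothesis". The null hypothesis is not written out. The four hypotheses are introduced with the statement "Each hypothesis examines part of the mechanism underpinning intervention impact on medication continuity".

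The SAP, dated 5/19/2022, opens with "The results of the Web Based Tools study will be assessed as described in this document". Its two working hypotheses concern medication continuity and the UTBC factors; the 80% hypothesis is not among them. SAP 1.3 lists "Fidelity to intended use of intervention components during the 4-month trial" separately from the primary and secondary outcomes. SAP 2.3.4 summarises this measure by its mean and its range, with no confidence interval, 80% threshold or test. The SAP text available does not mention that the protocol rule and interval have gone.

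**The concern.** To support a claim that the mean exceeds 80%, the data must exclude means of 80% or less, so the lower confidence limit has to lie above 80%. The protocol rule looks at the other end of the interval. It is met when 80% is merely compatible with the data, yet the result is to be called a rejected null. It also rewards imprecision: a smaller sample or more variable use widens the interval, so it reaches 80% from a lower mean.

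If the sentence were applied, a mean several points below 80% could be reported as support for use above 80%, in one of the four hypotheses by which the trial examines its mechanism. The SAP avoids that claim but loses the measure of precision, because a range shows how individuals differ and not how well the mean is known. A reader with both documents cannot tell whether an 80% verdict will be given, or by what rule.

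**Working it through.** **Plan's own figure.** There is none to reproduce. The Power and Sample Size section covers only the exploratory between-group comparison under Hypothesis #3; no error rate, power or SD is given for fidelity.

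**Inputs.**
- Threshold 80% and a two-sided 95% interval for the mean: protocol, Hypothesis #1.
- n = 22: protocol, recruitment section. n = 20: SAP section 1 ("We planned to enroll a total of 20 adolescents").
- n = 18 as a sensitivity case: Power and Sample Size plans for 36 of 44 retained over two groups, and 36/2 = 18.
- SD of the fidelity proportion: not in the documents. Assumed 10, 20 or 30 percentage points.

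**Step 1: what the rule means.** The interval is m ± t(0.975, n−1) × s/√n, where m is the observed mean and s the sample SD. It includes a value of 80 or more if and only if m + t × s/√n ≥ 80.

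**Step 2: does any null make the rule valid?**
- Null: mean at or below 80%. The rule rejects whenever 80% is not excluded, which is no evidence against this null.
- Null: mean at or above 80%. The rule rejects when the data agree with the null.
- Null: mean equal to 80%. The rule rejects when the interval contains the null value.

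None is valid. Only the first matches the stated hypothesis.

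**Step 3: error at the boundary.** At a true mean of 80, the chance that the upper limit falls below 80 is 2.5% under normality, so the rule rejects with probability 1 − 0.025 = 97.5% for any n or SD. Requiring the lower limit to exceed 80 rejects 2.5% of the time.

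**Step 4: lowest observed mean that passes**, 80 − t × s/√n. For n = 22 and s = 20: 80 − 2.080 × 20/4.690 = 80 − 8.9 = 71.1.

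| n | SD 10 | SD 20 | SD 30 |
|---|---|---|---|
| 22 | 75.6 | 71.1 | 66.7 |
| 20 | 75.3 | 70.6 | 66.0 |
| 18 | 75.0 | 70.1 | 65.1 |

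**Step 5: chance of passing when the true mean is below 80.** This is P(T ≥ −t(0.975, n−1)), where T is noncentral t with n−1 degrees of freedom and noncentrality √n(μ − 80)/σ. For n = 22, μ = 75, σ = 20, the noncentrality is 4.690 × (−5)/20 = −1.17 and the probability is 80.0%.

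| True mean | n | SD 10 | SD 20 | SD 30 |
|---|---|---|---|---|
| 75% | 22 | 39.1% | 80.0% | 88.8% |
| 75% | 20 | 43.6% | 81.5% | 89.5% |
| 70% | 22 | 0.6% | 39.1% | 68.0% |
| 70% | 20 | 1.1% | 43.6% | 70.7% |

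At n = 18 and SD 20 the figures are 83.1% (true mean 75%) and about 48% (true mean 70%).

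**Step 6: bounded data.** Proportions are bounded and probably skewed, so the rule was also simulated with beta-distributed fidelity (200,000 runs per cell). At a true mean of 80% it rejects 98.4–99.2% of the time (n = 20 or 22, SD 10–35). At 75% with n = 22 it rejects 38.7 / 85.0 / 93.7% of the time for SD 10 / 20 / 30. Normality is not what produces the problem.

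**The case against.** The strongest objection is that the SAP already settles the matter. It is the later document, says that it governs how results are assessed, omits the 80% hypothesis and treats fidelity descriptively. Followed alone, it yields no wrong claim. That stands, and it limits the harm to the case where the protocol sentence is applied. It does not remove the conflict, because the SAP neither withdraws the rule nor explains the loss of the interval. Front pages of the documents were not available, so a change history there cannot be excluded.

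A second objection is that asking whether 80% is plausible is a reasonable compatibility check for a small open-label study. It would be, if reported as one; the same sentence turns it into a rejected null.

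Third, the 97.5% follows from the definition of a 95% interval, and every figure below the boundary rests on an assumed SD. Both are true. The boundary figure is also the one that needs no assumed SD.

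Fourth, the analysed number is uncertain. The portal records use, but the denominator depends on answers to the assessment battery, so some families might have no fidelity value. Fewer subjects make the rule more lenient, as the n = 18 figures show.

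**Conclusion.** The concern holds. As written, the rule cannot support use above 80% under any reading of the unstated null. Its false-rejection rate at the boundary is 97.5% under normality and slightly higher with bounded data. At n = 22 and an assumed SD of 20 points, it accepts an observed mean as low as 71.1% and passes a true mean of 75% four times in five. Sizes below the boundary depend strongly on the SD, which the documents do not give: at a true mean of 70% and n = 22 the rate runs from 0.6% (SD 10) to 68.0% (SD 30).

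This should be fixed but is not critical. The primary outcome and safety are untouched, no progression rule depends on 80% fidelity, and a wrong claim arises only if the protocol sentence is used. If the SAP alone is followed, the loss is the promised precision estimate.

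**What to change.** Withdraw the decision rule: delete the protocol sentence that turns the interval into a rejection of the null, and record the withdrawal in SAP 2.3.4, for example:

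*Fidelity will be summarised as mean, 95% CI and full range. This replaces the decision rule under protocol Hypothesis #1; no claim that use exceeds 80% will be made.*

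Date this change and say that it was made after the study end date of 5/24/21 given in SAP 2.2.2. If the protocol can no longer be amended, disclose the change in the SAP and the final report.

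If a verdict on 80% is still wanted, support should require the lower limit of the two-sided 95% interval to exceed 80%, labelled post hoc for the same reason.

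The cost is a few sentences and no new data. The price is that there is no formal verdict on the 80% target. A t-based interval is also only approximate here: simulated coverage at a true mean of 80% is about 92.0–94.5% (beta data, n = 20 or 22, SD 10–35). The optional criterion is demanding. At n = 22 and SD 20 it needs an observed mean above 80 + 8.9 = 88.9%, and a true mean of 90% would meet it 60.9% of the time under normality (59.9% with beta data). With beta data its error rate at 80% is 4.0–7.2%, not 2.5%.

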9. Fidelity to intended use of intervention components: For each adolescent and parent, we will calculate the proportion of intervention components completed relative to the components that were recommended by the portal based on adolescent/parent responses to the assessment battery. For intervention components that are used once (e.g. trial on/off medicine), we will identify a portal data element to characterize intervention component completion. For intervention components that are used more than once (e.g. refill reminders, pill taking reminders, etc.), we will define "intended use" of the feature as use for at least 2 months since research suggests that, on average, it takes 2 months to develop a new habit (Lally et al. 2010). Mehealth for ADHD will capture and report on these data elements to characterize fidelity to the intended use of intervention components for each adolescent and parent.
10. Pre-intention factors of UTBC influencing medication continuity (Appendix G & H): Our measurement strategy for the adolescent and parent pre-intention factors closely follow well-developed procedures (Ajzen et al. 1981). We will use standard scales that have been used in hundreds of previous studies using the UTBC and closely related basic science theories. For example, an item to assess social norms would be "Most of the people who are important to me think I should take ADHD medicine regularly." Responses are on a 7-point scale from strongly agree (+3) to strongly disagree (-3). The internal consistency of items within each construct is good ($0.7 \leq \alpha \leq 0.9$) (Steele et al. 2005; Bentley et al. 2009; Cornelio et al. 2009; Boyko et al. 2011). For this study, we will assess pre-intention factors (i.e. expectations, social norms, self-concept/image, affect and emotions, and self-efficacy) framed around the behavior of "taking ADHD medicine regularly" following published methods (Francis et al. 2004) and informed by our prior qualitative research ([name] et al. 2009, 2012).

11. Behavioral Intentions (Appendix I & J): Teen and parent intention for teen to take ADHD medicine regularly will be measured using the standard measure of intention from the UTBC (Ajzen and Fishbein, 1981).

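### Hypothesis 2 concerns use of the intervention components, but the only predictor and criterion named for it is time point, and neither document relates use to UTBC change

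*Protocol*

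**What the plan says.** The protocol's DATA ANALYSIS section states Hypothesis #2 as: "Use of the intervention components will be related to improvements in the targeted UTBC factors". SAP section 1.1 repeats the idea as Working hypothesis 2, one of the two hypotheses it lists.

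The protocol then narrows the question in steps. The operational sentence is "we will test whether the intervention addressed the UTBC factors". The one predictor named is in "Model predictors will include a fixed effect indicator of time point (baseline or end of study". The decision rule is "A significant effect of time point in the expected direction would indicate UTBC factor improvement". Use of components appears in none of these three.

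Per-subject use is nevertheless a defined variable. Outcome measure 9 says: "For each adolescent and parent, we will calculate the proportion of intervention components completed relative to the components that were recommended by the portal".

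For Hypothesis #4, the other hypothesis phrased as a relation, the protocol does give an association model: "We will model the association between change in UTBC factor scores (independent variable) with change in medication continuity (dependent variable) using generalized linear model". Its conclusion, that a significant coefficient "would indicate changes in UTBC factor scores were associated with medication continuity improvement", matches what that hypothesis claims.

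**The concern.** All participants receive the intervention and there is no concurrent arm in the Hypothesis #2 analysis. The time coefficient is therefore the average change from baseline to end of study, whatever caused it. It bears on use only if one assumes that scores would not have moved without use, and this design cannot test that assumption. Under the stated rule, uncontrolled pre-post change could be reported as support for a hypothesis about use.

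This matters because the protocol says that each hypothesis examines part of the mechanism. The link from use to UTBC factors comes first and the link from UTBC factors to continuity (Hypothesis #4) second. The second has a matching model and the first does not. Under Scientific Rigor, the study is justified as a check on whether the mechanism is engaged and a larger trial is warranted, so a misattributed first link would carry into that decision.

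**Working it through.** **Step 1. Is use related to UTBC change anywhere else?**

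| Place | What it does | Links use to UTBC change? |
|---|---|---|
| Protocol, Hypothesis #1 | Mean use, 95% CI judged against 80%, and timing of use | No |
| Protocol, Hypothesis #2 | Time point as the only named predictor and criterion | No |
| Protocol, Hypothesis #3 | Continuity, paired t-test; exploratory external control comparison | No |
| Protocol, Hypothesis #4 | UTBC change against continuity change | No use term |
| Protocol, Exploratory analyses | Diversion and satisfaction | No |
| SAP 2.3.3 | Dependent variables only; no predictor or model | No |
| SAP 2.3.4 | Use as mean and full range | No |

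**Step 2. The plan's own figure.** The only sample-size calculation serves the exploratory between-group comparison under Hypothesis #3: 2 × (1.960 + 0.842)² × (16.5/15.7)² = 17.3, so 18 per group, as stated. No figure is given for Hypothesis #2.

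**Step 3. What can the time test tell apart?** The documents give no effect size, pre-post correlation or distribution of use, so all of these are assumed.

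- n = 20, the number in the protocol's STUDY DESIGN section and SAP section 1. The protocol's recruitment and sample-size sections give 22.
- Baseline score B standard normal; pre-post correlation 0.5, so the SD of change is 1.
- Standardized use U, normal and independent of B.
- Change = shift − 0.5·B + r·U + √(0.75 − r²)·E, with E standard normal noise and r the use-change correlation.
- Time test: one-sample t on change. Slope test: change on U, adjusted for B. A result counts as positive if it is in the expected direction at two-sided 5%. 40,000 runs per cell.

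*Scenario (i): shift of 0.5 SD unrelated to use.*

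| r | Time test positive | Adjusted slope positive |
|---|---|---|
| 0 | 56% | 2.5% |
| 0.3 | 57% | 31% |
| 0.6 | 56% | 94% |

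*Scenario (ii): no change without use, mean use 80%, SD 20 points.* The shift is r × 80/20 = 4r.

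| r | Time test positive | Adjusted slope positive |
|---|---|---|
| 0 | 2% | 3% |
| 0.1 | 40% | 7% |
| 0.2 | 92-93% | 15% |
| 0.3 | over 99% | 31% |

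A rerun with a new seed agreed to within about one percentage point.

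So an observed 0.5 SD time effect fits a use slope of zero (scenario i). It fits equally a slope of 0.5/8 = 0.0625 SD per 10 points of use, if all change comes from use and mean use is 80%.

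**Step 4. How precise would a use slope be?**

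- The correlation needed for 80% power with the adjusted slope is 0.54, 0.51 and 0.49 at n = 18, 20 and 22.
- The 95% CI half-width per 10 points of use at n = 18, with SD of use 20 points, is 2.131 × √0.75 × 10/(20 × √17) = 0.22 SD of change. It is 0.45 and 0.15 for SDs of 10 and 30 points.
- Against the slope of 0.0625 from Step 3, 0.22 is about 3.6 times as large.
- Multiplicity: five pre-intention factors, one barrier total and four barrier subscales, for two reporters, give 10 × 2 = 20 slopes. If these were independent and all null, the chance of at least one positive in the expected direction is 1 − 0.975²⁰ = 40%.

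**The case against.** The best defence is that Hypothesis #2 is a target-engagement test with loose wording. Families get the new features only when the trial starts, so baseline versus end of study is also before versus after access, and the stated aim is to see whether the mechanism is engaged. On that reading the time effect is the right quantity, and what remains is the ordinary limit of a declared open-label, single-arm design. This largely stands for pre-post change. It does not turn access into use: Hypothesis #1 exists because use may fall short of what is recommended.

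A second objection also stands. If the hypothesis is true in the form of scenario (ii), the planned time test is far more sensitive than the slope (92-93% against 15% at r = 0.2). The slope is no strong replacement.

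The simulation has limits too. The flat 56-57% follows from making the shift independent of use. Normal use with mean 80% and SD 20 puts about 16% of values above 100%. Use may also depend on baseline, because recommendations come from the assessment battery. The figures illustrate the logic and do not measure harm in this trial.

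Three stronger readings are tempting, and the documents do not support them.

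- A reader might infer that a use term is ruled out. The phrase "Model predictors will include a fixed effect indicator of time point (baseline or end of study" is not exhaustive; the point is that no other predictor is named and the decision rule rests on time.
- A reader might infer that the time effect says nothing about use. High use with no UTBC change would count against the hypothesis, so the evidence is weak rather than absent.
- A reader might see a further gap because the protocol says "we will assess pre-intention factors (i.e. expectations, social norms, self-concept/image, affect and emotions, and self-efficacy", while no component heading names self-efficacy as a target. The protocol's Background says that self-efficacy probably reflects experience with the other factors, so it need not be a direct target.

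**Conclusion.** The mismatch is real. Both documents state a relation between use and UTBC improvement, the only named predictor and criterion is time point, and nothing else in either document supplies the link. This rests on the text and needs no numerical assumption.

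The weight is minor to moderate. UTBC change is a secondary outcome, and nothing here touches the primary outcome, the sample size or safety. What is at risk is one conclusion: that use of the components was related to UTBC change, when only pre-post change was examined. The simulated percentages depend wholly on the assumed inputs. They show that the time test cannot separate change due to use from change unrelated to it, and that a use slope at this sample size would be imprecise.

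**What to change.** **Main change.** Report the Hypothesis #2 time effect as within-person pre-post change in the UTBC factors and nothing more. Keep the hypothesis as stated on record, and draw no conclusion about use from the time effect. If no use analysis is run, state that the relation with use was not tested. This costs a sentence or two in the report.

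**Optional and exploratory.** Regress each UTBC change score on the per-subject overall proportion of recommended components used, adjusted for the baseline score. Pair adolescent use with adolescent scores and parent use with parent scores. Report slopes with 95% CIs and the number of slopes tested. Label the analysis post hoc if it is added after follow-up ended: SAP version 1.1 is dated 5/19/2022, and its section 2.2.2 gives a study end date of 5/24/21.

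The option costs one SAP paragraph and up to 20 small models on data the protocol already collects. Its downsides should be stated with it: wide intervals at 18 to 22 subjects, self-selected use (motivation may drive both use and change), possible range restriction if use is as high as Hypothesis #1 expects, and multiplicity.
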